Study Protocol and Statistical Analysis Plan

Study Title: Effects of Daily Supplementation of 5-HTP on Body Composition, a Randomized Investigation

Protocol Version 2

Document Date: 01/03/22

Protocol ID# 102

Principal Investigators:

[name] PhD FNCSA FISSN CSCS

[name] MS RD

Nova Southeastern University

Protocol name: Effects of Daily Supplementation of 5-HTP on Body Composition, a
Randomized Investigation
Protocol Version 2
Document Date: 01/03/2022
Principal Investigators: [name] PhD FNCSA FISSN CSCS and [name] MS RD

5 HTP Study Protocol Table of Contents

| | |
|----------------------|---|
| Protocol Signature | 3 |
| Abbreviations | 3 |
| Abstract | 4 |
| Background | 4 |
| Study Objectives | 5 |
| Study Methods | 5 |
| Missing Data | 6 |
| Statistical Analysis | 6 |
| Summary of Data | 6 |
| FDA Reporting | 6 |

Protocol name: Effects of Daily Supplementation of 5-HTP on Body Composition, a
Randomized Investigation

Protocol Version 2

Document Date: 01/03/2022

Principal Investigators: [name] PhD FNCSA FISSN CSCS and [name] MS RD

PROTOCOL SIGNATURE

I confirm that I have read this protocol, and I will conduct the study as outlined herein and according to the ethical principles stated in the latest version of the Declaration of Helsinki, and the applicable laws and regulations of the federal government. I will promptly submit the protocol to the IRB for review and approval. I understand that any modification made during the course of the study must first be approved by the IRB prior to implementation except when such modification is made to remove an immediate hazard to the subject.

List of Abbreviations

| Abbreviation or Term | Definition/Explanation |
|-----------------------------|---|
| 5-HTP | 5-Hydroxytryptophan |
| PLA | Placebo |
| SSRIs | Selective serotonin reuptake inhibitors |

Protocol name: Effects of Daily Supplementation of 5-HTP on Body Composition, a Randomized Investigation

Protocol Version 2

Document Date: 01/03/2022

Principal Investigators: [name] PhD FNCSA FISSN CSCS and [name] MS RD

Abstract

The purpose of this investigation was to determine the effects of supplementing with 100 mg daily of 5-Hydroxytryptophan (5-HTP) on indices of body composition in exercise-trained men and women.

Specific Aims:

Aim 1: Anthropometric measurements will be collected to determine if 5-HTP supplementation can induce changes in body composition.

Aim 2: Self-reported dietary intake will be tracked using MyFitnessPal to determine if daily 5-HTP supplementation influences eating behaviors.

Aim 3:

Methods: Subjects were randomized into a treatment (100 mg 5-HTP daily; CLEANMOOD™) or a placebo (maltodextrin). Body composition was assessed pre- and post-treatment after eight weeks via a multi-frequency bioelectrical impedance device (InBody® 270). Subjects were instructed to not change their training or eating habits; moreover, they were instructed to track their diet ~2-3 days per week using a mobile app (MyFitnessPal).

Hypothesis:

Compared to placebo, daily supplementation with 5-HTP will result in changes in body composition.

Background

5-Hydroxytryptophan (5-HTP) is an amino acid and intermediate metabolite of L-tryptophan. 5-HTP crosses the blood-brain barrier, stimulating serotonin (5-hydroxytryptamine) receptors in the central nervous system.[1, 2] Increasing serotonin levels may lead to changes in eating behavior, such as reduced calorie intake and increased satiety.[3, 4] When consumed orally, 70% of 5-HTP is delivered to the bloodstream. Once absorbed, 5HTP supplementation increases serotonin production and other brain chemicals such as melatonin, endorphins, dopamine, and norepinephrine. Supplementing with 5-HTP is linked to appetite suppression, improved sleep quality and decreased feelings of anxiety and depression. [2, 3, 5-8] 5-HTP has been posited to be an effective weight-loss aide due to its anorexigenic effects; however, little data exists and virtually all investigations have studied overweight or obese subjects. Cangiano et al. showed that 5-HTP supplementation influenced energy intake in non-insulin dependent diabetic subjects. Subjects receiving 5-HTP consumed less energy via decreased consumption of fats and carbohydrates resulting in weight loss.[5] Another study observed the effects of a 5-HTP containing supplement on body composition in overweight females. Subjects were instructed to reduce their energy intake moderately. Following 4-weeks of 5-HTP supplementation, significant reductions in BMI, arm circumference and hip circumference were observed. Increased feelings of satiety were greater in the supplement group when compared to placebo.[8] Ioannou and Williams examined the effects of 5-HTP intake on brain activity as it relates to food sensitivity in healthy individuals.[6] Subjects were randomly assigned to a 5-HTP or vitamin C supplement group. This investigation discovered that 5-HTP intake influences areas of the brain related to macronutrient selection and increased awareness of the body's internal physiological needs. The vitamin C group was more responsive to high caloric and fatty foods compared to the 5-HTP group. This study suggests that 5-HTP intake can influence macronutrient intake as well as modulate eating behaviors. Presently, there

Protocol name: Effects of Daily Supplementation of 5-HTP on Body Composition, a Randomized Investigation

Protocol Version 2

Document Date: 01/03/2022

Principal Investigators: [name] PhD FNCSA FISSN CSCS and [name] MS RD

are no studies that have assessed the effects of 5-HTP in exercise-trained individuals. Therefore, the purpose of this investigation was to determine the effects of supplementing with 100 mg daily of 5-hydroxytryptophan (5-HTP) on indices of body composition in exercise-trained men and women.

Study Objectives

Primary Objective

To assess changed in body composition.

Secondary objective

To assess any changes in dietary intake.

Study Methods

Study Design

This study followed a placebo (PLA)-controlled, double-blind and parallel-group design.

Study population

61 physically active, healthy, adults (>18) were volunteered for this study.

Inclusion-Exclusion Criteria

Inclusion Criteria:

- Healthy or free of disease
- Minimum of 1 year of regular physical activity. Regular physical activity is defined by a minimum of 150 minutes of aerobic activity or performing muscle-strengthening exercises at least 2 days a week.

Exclusion Criteria:

- Physically inactive
- Regularly used sleep aids of any kind
- Currently taking selective serotonin reuptake inhibitors (SSRIs) and/or 5-HTP containing supplements.

Discontinuation or Withdrawal from Study

The reasons a subject may discontinue or be withdrawn from the study include, but are not limited to, adverse events, non-compliance or personal request to no longer participate in study.

Randomization and Blinding

All subjects and investigators were blinded. The supplement and placebo were in similar in capsule appearance and were packed in unmarked packaging. The research team were unaware of the subject assignments until completion of the entire study.

Intervention and Placebo

The dietary supplement (100 mg of 5-hydroxytryptophan; CLEANMOOD™) was provided by NURA™ (Irvine, California USA). CLEANMOOD is an organic 5-Hydroxytryptophan (5-HTP) ingredient. The placebo consisted of maltodextrin in a capsule. Subjects were instructed to consume one capsule daily at their convenience for 8 weeks.

Data Collection Schedule

Subjects were instructed to arrive at the laboratory after a 3-hour fast. All pre and post-testing occurred between 1200 and 1700 hours.

Protocol name: Effects of Daily Supplementation of 5-HTP on Body Composition, a Randomized Investigation
 Protocol Version 2
 Document Date: 01/03/2022
 Principal Investigators: [name] PhD FNCSA FISSN CSCS and [name] MS RD

| Study Visit | Pre/Baseline | Post |
|--|--------------|------|
| Informed Consent | x | |
| InBody | x | x |
| Vitals | x | x |
| Supplement Instruction | x | |
| Connect MyFitnessPal account | x | |
| Asses dietary intake via MyFitnessPal | x | x |
| Asses Compliance (number of pills remaining) | | x |

Missing Data

Thirteen subjects were excluded from the data set due to lack of compliance or failure to complete the study.

Statistical Analysis

All data is presented as the mean+SD. GraphPad (Prism 8) software was used for statistical analyses. A t-test was used to determine if statistically significant differences ($p < 0.05$) existed between the delta scores of the treatment versus the placebo.

Summary of Study Data

Demographic and Baseline

The characteristics of the treatment and placebo groups were as follows (age: 5-HTP 30 ± 10 , placebo 29 ± 11 ; height cm: 5-HTP 171.0 ± 8.7 , placebo 167.7 ± 15.0 ; body mass kg: 5-HTP 72.9 ± 13.4 , placebo 69.1 ± 11.9). Subjects in this investigation were exercise-trained (years of training: 5-HTP 14 ± 10 , placebo 16 ± 11 ; hours of resistance training per week: 5-HTP 5 ± 2 , placebo 5 ± 3 ; hours of aerobic training per week: 5-HTP 5 ± 4 , placebo 6 ± 5).

FDA Annual Reporting

This study is not a FDA regulated drug or device, therefore there are no annual reporting requirements to the FDA.

Clinical Trial Data Bank

The study will be registered on <http://clinicaltrials.gov> and the NCI CTRP (Clinical Trials Reporting Program) by the Clinical Trials Office.

References

1. Birdsall, T.C., *5-Hydroxytryptophan: a clinically-effective serotonin precursor*. *Altern Med Rev*, 1998. **3**(4): p. 271-80.
2. Maffei, M.E., *5-Hydroxytryptophan (5-HTP): Natural Occurrence, Analysis, Biosynthesis,*

Protocol name: Effects of Daily Supplementation of 5-HTP on Body Composition, a
Randomized Investigation

Protocol Version 2

Document Date: 01/03/2022

Principal Investigators: [name] PhD FNCSA FISSN CSCS and [name] MS RD

- Biotechnology, Physiology and Toxicology*. Int J Mol Sci, 2020. **22**(1).
3. Halford, J.C., et al., *Serotonergic anti-obesity agents: past experience and future prospects*. *Drugs*, 2011. **71**(17): p. 2247-55.
 4. Yabut, J.M., et al., *Emerging Roles for Serotonin in Regulating Metabolism: New Implications for an Ancient Molecule*. *Endocr Rev*, 2019. **40**(4): p. 1092-1107.
 5. Cangiano, C., et al., *Effects of oral 5-hydroxy-tryptophan on energy intake and macronutrient selection in non-insulin dependent diabetic patients*. *Int J Obes Relat Metab Disord*, 1998. **22**(7): p. 648-54.

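### The plan does not say which body-composition variable is primary, how many are tested, or what result would support the hypothesis

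*Combined protocol and SAP*

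**What the plan says.** Study Objectives gives the primary objective as "To assess changed in body composition". The Hypothesis section is equally general: "Compared to placebo, daily supplementation with 5-HTP will result in changes in body composition". The purpose sentence, in the Abstract and again in the Background, concerns effects "on indices of body composition in exercise-trained men and women", in the plural and without a list. Aim 1 speaks only of anthropometric measurements.

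Several parts of the analysis are specified. The Abstract's Methods paragraph gives the instrument and timing: "Body composition was assessed pre- and post-treatment after eight weeks via a multi-frequency bioelectrical impedance device", the device being the InBody 270. Statistical Analysis prescribes a t-test at p < 0.05 to see whether differences "existed between the delta scores of the treatment versus the placebo". Sidedness is not stated.

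Body composition is ranked above diet, whose secondary objective is "To assess any changes in dietary intake". There is no ranking within body composition. Body mass appears only as a baseline characteristic in the data summary. BMI and circumferences appear only in the Background's account of a cited study.

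**The concern.** The primary objective names a domain that one device can summarise in several ways. The only testing rule refers to delta scores without saying of what. Two analysts holding the same data could each follow this plan, pick different indices and reach opposite conclusions on the trial's only hypothesis.

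A reader of the results therefore cannot tell whether a reported effect on body composition is the planned result or one of several indices that happened to cross 0.05. In the second case, the nominal 5% does not describe the chance of a false claim about the hypothesis.

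**Working it through.** **Is the variable named anywhere?** No. The objective, hypothesis, Aim 1, purpose sentence, visit table (which lists only InBody) and Statistical Analysis section all stay generic.

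**Is there a figure of the plan's own to reproduce?** Only the 0.05 threshold. No sample-size calculation, effect size or SD for change is given.

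**Inputs from the documents.** 61 enrolled and 13 excluded, so 61 - 13 = 48 analysed. Threshold 0.05. Baseline body mass 72.9 ± 13.4 kg (5-HTP) and 69.1 ± 11.9 kg (placebo).

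**Assumptions, not in the documents.** 24 per arm; two-sided unpaired t-tests on change; any p < 0.05 counts as support. The indices are drawn from body mass, fat mass, fat-free mass and percent fat. Fat-mass and fat-free-mass changes have equal SDs (1.5 kg) and correlation -0.5 to +0.3. Body-mass change is their sum. Percent fat is computed from baseline body mass 71 (SD 12.7) kg and baseline percent fat 20 (SD 7).

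**Reference values if k indices were independent.** Risk = 1 - 0.95^k:
- k = 1: 5.0%
- k = 2: 1 - 0.9025 = 9.75%
- k = 3: 1 - 0.8574 = 14.3%
- k = 4: 1 - 0.8145 = 18.5%

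**Linked indices.** Chance of at least one p < 0.05 under no effect, 40,000 simulated trials per setting:

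| Fat/lean change correlation | Two indices (six pairs) | Three indices (four triples) | All four |
|---|---|---|---|
| -0.5 | 6.5–9.7% | 10.2–12.6% | 13.4% |
| -0.3 | 6.2–9.5% | 10.1–12.2% | 13.0% |
| 0 | 6.4–9.8% | 9.7–12.0% | 12.7% |
| +0.3 | 6.6–9.7% | 9.4–11.4% | 12.1% |

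The simulation standard error near 10% is about 0.15 percentage points, so the 9.8% entry does not conflict with the 9.75% reference. With all four indices, a 20/28 split between arms gives 12.0–13.1%.

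**Does Holm on a complete list hold the error?** Yes. A false claim under no effect requires the smallest p to fall below 0.05/k. Across all sets of two to four this happened in 2.8–5.0% of trials, including runs with lean/fat change-SD ratios of 0.5 to 1.5. If four indices are analysed but only the best two are kept and Holm is applied to those, the risk is 6.3–6.9% (equal SDs). The list must therefore not be shortened after unblinding.

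**Power cost of Holm.** Noncentral t, 46 degrees of freedom, noncentrality d × √(24/2). A difference of d = 0.826 SD has 80% power at 0.05. At the strictest Holm step:

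| Indices | Threshold | Power at d = 0.826 | d for 80% power |
|---|---|---|---|
| 1 | 0.05 | 80% | 0.83 |
| 2 | 0.025 | 71% | 0.92 |
| 3 | 0.0167 | 65% | 0.96 |
| 4 | 0.0125 | 61% | 1.00 |

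**The case against.** The strongest reply is that much of the analysis is defined: device, both time points, between-group comparison of changes, test and threshold. That stands. A reader might infer that the hypothesis has no test at all, but the text does not support this. The gap is confined to which variable, how many, and what counts as success.

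Second, inflation needs more than one index tested and any one counting. The plurals suggest several indices but do not prove it, and delta scores may be plural only because there are many subjects. This also stands, so the percentages describe a scenario and are not a measurement of this trial.

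Third, Randomization and Blinding says "The research team were unaware of the subject assignments until completion of the entire study". That protects measurement, but it does not show that an index was fixed in advance. A reader might infer the opposite, that the endpoint was chosen after unblinding, because this version already reports exclusions and baseline data by arm. The documents do not show that either. The Clinical Trial Data Bank section says "The study will be registered on" a public registry, and a dated entry there might settle the question.

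Fourth, one might demand Holm across every InBody output. The documents never list that output, so the family would remain undefined and could be long. Under the same assumptions, power at the strictest step falls to about 38% for 20 indices and 33% for 30. That objection is sound, and Holm should be optional.

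**Conclusion.** The point holds as a limited gap: the primary variable, the number of variables tested and the criterion for support are unstated, and there is no multiplicity rule within body composition. The false-claim risk is 5% if one index was fixed before unblinding. It is above 5% if several are each tested at 0.05 and any one counts: roughly 6–10%, 9–13% and 12–13% for two, three and four linked indices under the assumed 24 per arm, equal change SDs and correlations of -0.5 to +0.3. The documents do not determine which case applies.

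The omission itself is certain, while the size of any inflation is not. Because the text is largely retrospective, new wording cannot create pre-specification; it can only document it or admit its absence. The fix is rated a cheap improvement.

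**What to change.** 1. If a record dated before unblinding names one primary index or a fixed list, cite it in Statistical Analysis with its date. Test the single index at two-sided 0.05, or apply Holm across the fixed list. A registry entry qualifies only if its date precedes unblinding.
2. Otherwise, label the body-composition results exploratory. Report every index analysed, with units, the between-group difference in change (post minus pre) and a 95% CI. Do not present an unadjusted p < 0.05 on any single index as confirming the hypothesis.
3. As an alternative to step 2, apply Holm across the complete list of indices analysed, provided the list is stated in full and not shortened after unblinding.

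Leave the dietary objective as it stands.

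The work is wording plus, at most, a re-run of existing data. The exploratory label gives up any confirmatory claim. Holm lowers power per index from 80% to about 71%, 65% and 61% at its strictest step for two, three and four indices, assuming 24 per arm.

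### The eligibility criteria admit women over 18 but do not exclude pregnancy or breastfeeding, and no visit asks about either

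*Combined protocol and SAP*

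**What the plan says.** The stated purpose, in the Abstract and at the end of the Background, concerns "indices of body composition in exercise-trained men and women". Study population states that "61 physically active, healthy, adults (>18) were volunteered for this study", with no upper age limit.

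Inclusion-Exclusion Criteria has two inclusion items: "Healthy or free of disease", and at least one year of regular physical activity. It has three exclusions: "Physically inactive", "Regularly used sleep aids of any kind", and current use of SSRIs or supplements containing 5-HTP.

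The table under Data Collection Schedule lists consent, InBody, vitals, supplement instruction, MyFitnessPal connection, dietary intake and a pill count. It has no row for pregnancy or breastfeeding at either visit.

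On the product, the Background states that "5HTP supplementation increases serotonin production and other brain chemicals such as melatonin, endorphins, dopamine, and norepinephrine". On age, Demographic and Baseline gives "age: 5-HTP 30 ± 10 , placebo 29 ± 11", by arm and with the sexes pooled.

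**The concern.** A site that applies the criteria literally has no ground for turning away a healthy, active woman who is pregnant or breastfeeding. She would take 5-HTP or placebo daily for eight weeks. The protocol describes the product as acting on several neurotransmitters, and it already screens out people taking SSRIs or other 5-HTP products. It does not say why exposure in pregnancy or during breastfeeding would be acceptable, and nothing shows that the question was considered.

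There is also a smaller analytic concern. The primary objective is change in body composition, measured by bioimpedance before and after eight weeks. Subjects are told to keep training and diet unchanged, so the design tries to hold other causes of change still. Pregnancy is a cause of change unrelated to the supplement. The Statistical Analysis section plans an unadjusted t-test on the change scores, so an affected value would enter as it stands.

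**Working it through.** **Does any text close the gap?**

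| Place in the document | Would it exclude or identify a pregnant or breastfeeding woman? |
|---|---|
| Health inclusion criterion | No. Neither state is a disease. |
| Activity inclusion criterion | No. An active woman meets it. |
| Three exclusions | No. They concern inactivity, sleep aids, and SSRIs or 5-HTP. |
| Visit table | No. There is no question or test at Pre or Post. |
| Discontinuation or Withdrawal | It could permit withdrawal, since the list of reasons is open, but it does not screen at entry and prompts nobody to ask. |

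Pregnancy, breastfeeding, contraception and pregnancy testing are not mentioned anywhere in the document.

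**How much could one affected subject move the comparison?** The plan has no figure to reproduce: it gives no sample-size calculation and no SD of change. What follows is an illustration.

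Inputs from the documents: 61 subjects (Study population) and 13 excluded from the data set (Missing Data), so 61 − 13 = 48 remain.

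Assumptions not in the documents:
- an equal split of the 48, so n = 48/2 = 24 per arm;
- one affected subject whose change is shifted by g = 1 to 5 kg;
- an SD of the change score, s, of 1 to 2 kg.

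Body mass stands in for whichever body-composition index is analysed, because the protocol names none as primary.

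Shift in her arm's mean = g/n:
- g = 1: 1/24 = 0.04 kg
- g = 5: 5/24 = 0.21 kg

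Standard error of the between-arm difference = s × √(2/n):
- s = 1: 1 × √(2/24) = 0.289 kg
- s = 2: 2 × √(2/24) = 0.577 kg

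Shift as a fraction of that standard error:
- smallest: 0.0417/0.577 = 0.07
- largest: 0.2083/0.289 = 0.72

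The outlying value also inflates the variance in her own arm, to about s² + g²/n. In the largest case this is 1 + 25/24 = 2.04. The standard error becomes √((1 + 2.04)/24) = 0.356 kg, and the ratio falls to 0.2083/0.356 = 0.59.

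**The case against.** The strongest case on the other side has five parts.

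- **The safety argument shows no harm.** Nothing in the documents addresses fetal or infant risk. This stands: a reader might infer a demonstrated hazard, and the documents do not support that. They support only an unexplained exposure, which is reason enough for a precaution.
- **The number and ages of the women are unknown.** A reader might take the mean age of about 30 as describing the women. It does not, because the figures are by arm with men and women pooled. That some women were of childbearing age is a fair inference. That any was pregnant or breastfeeding is not shown.
- **The effect on the result is small and is not bias.** This stands. A reader might infer that the treatment comparison is biased, but subjects were randomized, so affected women would fall in either arm by chance. The kilogram figures are assumptions, and that pregnancy changes body composition is general knowledge, not a statement in the protocol.
- **The point may be handled elsewhere.** The withdrawal list is open-ended, and the consent form is not in the text reviewed, so a warning there cannot be ruled out. Neither changes the stated criteria, which decide who is eligible.
- **The study appears to be finished.** Much of the text is in the past tense and baseline data are reported. If so, a new criterion cannot change who was exposed, and only the reporting part of the fix can be used.

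**Conclusion.** The gap holds on the text. The criteria admit pregnant and breastfeeding women, no visit identifies them, and no rationale for the exposure is given. This conclusion needs no numerical assumption and does not depend on how many women are affected.

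The effect on the analysis is secondary. Under the assumed 24 per arm, a 1 to 5 kg change in one subject and an SD of change of 1 to 2 kg, one case moves an arm mean by 0.04 to 0.21 kg, or 0.07 to 0.72 of a standard error. That is added noise or chance imbalance. It does not show that the trial's result was altered.

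**What to change.** Add one item to the exclusions: pregnant, breastfeeding or planning pregnancy during the study, by self-report. Ask it at the Pre visit, before Supplement Instruction. Ask again at Post for analysis purposes only, since by then the eight weeks of supplementation are over. If a pregnancy is reported, present the body-composition comparison with and without that subject.

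If enrolment is already complete, report the number of women in each arm, whether any pregnancy or breastfeeding was known at entry or during the eight weeks, and the same comparison with and without any affected subject.

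The cost is one criterion and one question at each of two existing visits, with no new procedure. The downsides are a very small loss of eligible volunteers, and that self-report can miss an unrecognised early pregnancy.

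### The withdrawal section does not separate stopping the supplement from leaving the study and does not require the week-8 scan after discontinuation, so outcomes may be missing for treatment-related reasons

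*Combined protocol and SAP*

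**What the plan says.** Under Study Methods, the section Discontinuation or Withdrawal from Study is one sentence: "The reasons a subject may discontinue or be withdrawn from the study include, but are not limited to, adverse events, non-compliance or personal request". Leaving the study is the only status it describes. There is no category for a subject who has stopped the capsules but is still followed.

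The other relevant places are:

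- **Outcome timing (Abstract, Methods):** "Body composition was assessed pre- and post-treatment after eight weeks via a multi-frequency bioelectrical impedance device". There is one measurement after baseline.
- **Data Collection Schedule:** the table has two columns, Baseline and Post, and no early-termination visit. InBody is marked in both. The compliance row, "Asses Compliance (number of pills remaining) | | x", is marked at Post only, so the capsule count and the outcome scan fall at the same visit.
- **Intervention and Placebo:** "Subjects were instructed to consume one capsule daily at their convenience for 8 weeks".
- **Statistical Analysis:** a t-test compares the arms on change from baseline, which needs a Post value for each analysed subject. No method is given for a missing Post value.
- **Missing Data:** "Thirteen subjects were excluded from the data set due to lack of compliance or failure to complete the study". No breakdown by arm or reason is given, and the section does not say how many of these subjects had a Post scan.

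**The concern.** This is a question of data collection. Adverse events and non-compliance are named as grounds for leaving the study, and both can depend on the assigned product. If such a subject leaves and is not asked back at week 8, the primary outcome is not measured. A broader analysis set chosen later cannot supply it.

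The comparison then moves from subjects as assigned towards subjects who tolerated and took the capsules, and randomisation no longer protects it. With 13 subjects already out of the data set, this is not hypothetical, although the documents do not show how many of them went unmeasured.

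**Working it through.** The plan gives no sample-size calculation, expected dropout or allocation ratio, so there is no design figure to reproduce.

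**Inputs.** From the documents: 61 subjects (Study population: "61 physically active, healthy, adults (>18) were volunteered for this study"), 13 excluded (Missing Data), and one capsule a day for 8 weeks. Assumed: 61 is the number randomised before exclusions, the arms were 30 and 31, and the spread of change is the same in excluded and retained subjects.

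**1. Share excluded.** 13/61 = 0.213, or 21%, leaving 61 - 13 = 48. The text does not say whether 61 precedes the exclusions. If it were the number left after them, the share would be 13/74 = 0.176.

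**2. How many of the 13 lack a scan.** Missing Data names two reasons. A subject found non-compliant by capsule count was at the Post visit, when the scan was also due. A subject who did not complete may not have been. With no split given, the number k without a scan can be anything from 0 to 13.

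**3. Precision.** Collecting the k missing scans multiplies the standard error by sqrt((61 - k)/61).

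- k = 0: 1.00, no gain
- k = 6: sqrt(55/61) = 0.95, about 5% narrower
- k = 13: sqrt(48/61) = 0.887, about 11% narrower, which is the maximum

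**4. Shift in the between-arm difference.** Let m1 and m2 be the shares excluded in the two arms, and let d be the mean change in excluded subjects minus that in retained subjects. Each all-randomised arm mean is the retained mean plus m × d. With the same d in both arms, including the excluded subjects therefore moves the difference by (m1 - m2)d.

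| Excluded, arm of 30 / arm of 31 | m1 - m2 | Shift |
|---|---|---|
| 0 / 13 | 0 - 13/31 | -0.42d |
| 6 / 7 | 0.200 - 0.226 | -0.03d |
| 9 / 4 | 0.300 - 0.129 | +0.17d |
| 13 / 0 | 13/30 - 0 | +0.43d |

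The near-zero result for an even split depends on d being equal in the two arms. If only 5-HTP leavers differ, say by 0.5 SD (assumed, with 30.5 per arm), the shift is:

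- even split: 6.5/30.5 × 0.5 = 0.11 SD
- 10 of the 13 on 5-HTP: 10/30.5 × 0.5 = 0.16 SD
- all 13 on 5-HTP: 13/30.5 × 0.5 = 0.21 SD

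These shifts are for all 13. The part due to non-collection concerns only the k subjects without a scan. The rest comes from excluding subjects who were measured.

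**5. What the capsule count can show.** Assuming 56 capsules (8 × 7; the number dispensed is not stated), 14 left over fits a subject who stopped at day 42 (56 - 14) and was 14 days off product at the scan. It equally fits a subject who missed one capsule in four throughout (14/56 = 25%). The count alone cannot tell these apart, and it exists only for subjects who attend.

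**The case against.** The strongest reply is that the withdrawal sentence is permissive. It says what may happen. It sets no compliance threshold, does not mention capsules, and does not forbid a Post scan. A reader might infer that missing capsules automatically ends participation and that the outcomes of these subjects were never collected. The documents support neither inference. The capsule count and the scan share a visit, and Missing Data describes removal from a data set, so some or all of the non-compliant subjects may have been scanned first. If all 13 were scanned, collection was complete and the fault lies wholly in the exclusion.

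Nor can it be said that subjects who reported missed capsules earlier were removed before the scan, because no interim contact is described. Non-compliance is also undefined. The Abstract gives further instructions on training, eating habits and diet logging that it might cover.

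Finally, most of the document is in the past tense, so new wording about visits cannot recover measurements already missed.

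All of this stands, and it limits the claim to a gap through which outcomes may be lost. It does not close the gap. Nothing requires the week-8 scan after discontinuation, failure to complete is named as a separate reason for exclusion, and a subject without a Post value cannot enter the planned test.

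**Conclusion.** The concern holds as a gap in the plan. A subject who stops for an adverse event or is withdrawn for non-compliance need not be scanned at week 8, and the reason may be related to treatment.

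The size cannot be fixed from the documents, because neither k nor the split by arm is reported. The loss of precision is small, at most about 11% of the standard error. Bias matters more: it ranges from negligible to about 0.4d in either direction under a common d. These bounds rest on 61 being the number randomised before exclusions and on arms of 30 and 31. The value of d is unknown.

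**What to change.** 1. **First, since the study appears to have been run:** retrieve any Post scans taken on the 13 excluded subjects. Report the 13 by arm, reason and scan availability. Include those with scans in an all-randomised analysis.
2. **In the protocol wording, and for any subject still in follow-up:** separate stopping the capsules from withdrawing consent to follow-up. Do not let non-compliance alone end outcome collection. Ask every randomised subject who has not withdrawn consent to attend the week-8 Post visit, whatever their capsule use. At that visit, record the date of the last capsule beside the count.

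This concerns data collection only and says nothing about who should stop the supplement.

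The cost is a search of existing records and one extra table, then a paragraph of wording and one added field at an existing visit. There will be a few more Post visits to chase. The estimate will include time off capsules and so may be slightly smaller. The wording change cannot recover scans that were never taken.
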